4.3.2.1. Stopping Rules

4.3.2.1.1. Individual Subject Stopping Rules

Participation in the clinical study may be discontinued by an Investigator (or delegate) in charge of the study or by the Sponsor for any of the following reasons, but not limited to:

- AEs (including if a subject develops any significant illness or needs to undergo any major surgery during course of the study) or laboratory abnormalities that would put the subject at risk to continue in the opinion of the Investigator and/or the Sponsor

- Subject non-compliance (including any violation of protocol requirements which may affect the study outcome)

4.3.2.1.2. Cohort Stopping Rules

If any of the following safety concerns are observed, dosing of all subjects at the given dose level or higher will be suspended/halted and all available data will be evaluated by the SRC. Dose continuation (remaining subjects within a cohort or remaining dosing for a subject) or escalation should not proceed for any of, but not limited to, the following reasons:

- If 1 kratom-related SAE occurs in a cohort
- Moderate or severe AEs in 50% of the subjects in the cohort or more

Dose escalation will be discussed during the SRC meeting and may be stopped depending on Principal Investigator's or Sponsor's decision.

4.3.2.1.3. Trial Stopping Rules

Clinical trial stopping rules:

- If 2 kratom-related SAEs occur in a cohort
- Occurrence of 1 death attributable to kratom

4.4. Lifestyle and/or Dietary Requirements

- Subjects will be prohibited from consuming food or beverages containing grapefruit and/or pomelo for 7 days prior to dosing and during the study.
- Subjects will be prohibited from consuming alcohol for 48 hours prior to dosing and during the study. Throughout the study (including the Follow-Up Visit), in case of any doubt about alcohol consumption, a test for alcohol may be performed if requested by an Investigator.
- Subjects will be prohibited from consuming food or beverages containing xanthines (i.e., tea, coffee, cola drinks, energy drinks or chocolate) for 48 hours prior to dosing and during the study.
- Subjects will be prohibited from consuming all recreational drugs (including cannabis) from the time of screening and for the duration of the study.
- Subjects will eat only the food provided by the study site during confinement at the clinical site.
- During the study, subjects who are smokers should not smoke more than the equivalent of 20 cigarettes per day. Subjects will abstain from smoking for 1 hour prior to and until 8 hours after study drug administration.
- Subjects will be asked to refrain from driving, operating machinery, or engaging in hazardous activities until they and an Investigator are convinced the study drug is not impairing their judgment and/or ability to perform skilled tasks.

- Female subjects of childbearing potential will have to take appropriate measures to prevent pregnancy as described in Section 4.1. It is the participant's responsibility to notify the clinical site if a pregnancy occurs from the end of their study participation until 30 days after study drug administration.
- Male subjects will be expected to use an acceptable contraceptive regimen and not to donate sperm as described in Section 4.1.

4.5. Concomitant Treatment

In addition to the drugs prohibited as per the exclusion criteria (Section 4.2), subjects will also be prohibited from taking any over-the-counter products for 7 days prior to dosing and during the study, unless deemed acceptable by an Investigator.

Except for medication which may be required to treat AEs, no other treatment or medication other than the study drugs will be allowed from the first dosing until all study activities and evaluations have been completed.

Systemic contraceptives and hormone replacement therapy are permitted for female subjects.

Subjects will be instructed to notify the study site about any new medications taken after the start of the study treatment. All medications and significant non-drug therapies (including physical therapy and blood transfusions) administered after the subject has received the study treatment must be listed in the subject case report form (CRF). The drug name and dose taken will be noted. An Investigator or delegate and/or the Sponsor will decide whether the subject will be permitted to remain in the study, depending on the drug used, the time of drug intake, etc.

5. STUDY TREATMENTS

5.1. Investigational Products

All IPs will be provided by the Sponsor.

5.1.1. Kratom 500 mg Capsules

Kratom capsules consist of 500 mg kratom leaf powder filled into light blue gelatin capsules. Kratom 500 mg capsules are manufactured by Sun Distribution, Super Organics for oral administration.

5.1.2. Placebo

Placebo capsules made with microcrystalline cellulose will be matched to Kratom 500 mg Capsules. The weight will be matched to the Kratom 500 mg Capsules and the composition will be the same, including excipients.

5.2. Investigational Product Management

5.2.1. Packaging, Labeling and Dispensing

The Sponsor will be responsible for ensuring that the IPs are manufactured in accordance with applicable current Good Manufacturing Practice regulations and requirements.

The IPs will be labeled according to the requirements of local law and legislation. The IPs will be dispensed by the clinical site's pharmacy, unless the Sponsor supplies the pharmacy with prelabeled individual dosing samples.

5.2.2. Storage and Handling

All study drugs will be shipped from the client or client resources to the clinical site's pharmacy. Storage and handling conditions are described in the Investigator's Brochure of kratom.¹

The clinical site's pharmacy will maintain an inventory record of the IPs received, stored (in a secure restricted area), and dispensed. IPs will be provided to study subjects only.

5.2.3. Method of Assigning Subjects to Treatment Groups

In each cohort, subjects will be randomized 6:2 (active: placebo). The clinical site will generate the randomization code with a computer program according to the study design, the number of subjects and the number of treatments. Once generated, the randomization code will be final and will not be modified.

5.2.4. Blinding

The randomization code will not be available to the personnel of the bioanalytical facility until the bioanalytical phase of the study has been completed. The treatment assignment (active or placebo) will not be known by the study participants. Study participants will be informed of the dose range they could receive but will not be informed of the actual dose assigned to them.

Furthermore, the randomization code will not be available to the Investigator and clinical staff involved in the collection, monitoring, revision, or evaluation of AEs, as well as clinical staff who could have an impact on the outcome of the study including the pharmacokineticist (or delegate) and biostatistician, until all the CRFs have been approved and signed and the bioanalytical phase of the study has been completed.

The preparation and/or administration of the products will be done by designated personnel who are not directly involved in the clinical aspects of the trial.

The randomization code must not be broken except in emergency situations where the identification of a subject's study treatment is required by an Investigator for further treatment to the subject or to complete a SAE report. Randomization information will be held by designated individual(s). The date and reason for breaking the blind must be recorded.

The results of the PD analyses will be made available only to the personnel responsible for evaluating the safety data before proceeding with the next dose level.

5.2.5. Study Drug Accountability

Complete and accurate inventory records of all study drugs will be maintained. This includes acknowledgment of receipt of each shipment of study product (quantity and condition), subject dispensing records, and returned or destroyed study product.

At the conclusion of the study, all unused IPs and all medication containers will be returned to the Sponsor unless the Sponsor has approved other arrangements. Drug accountability will be performed at the completion of the trial.

5.3. Administration of Study Drug

Study drug will be administered in the morning. The date and time of each dose will be recorded. For each subject, all scheduled postdose activities and assessments will be performed relative to the time of study drug administration.

Thirty (30) minutes after the start of a high-fat breakfast (refer to Section 5.4 for details), an oral dose of the assigned formulation will be administered to subjects with approximately 240 mL of water at ambient temperature. Considering the high number of capsules to be taken for certain cohorts, an additional 240 mL of water will be allowed if required. Time of dosing will be set equal to the time when the first capsule is administered to the subject. The complete dosing procedure must be completed within 5 minutes. Dosing procedures done up to 2 minutes outside the allowed time window will not be considered as protocol deviations but will be documented. The start and end times, as well as the volume of water ingested during drug administration will be recorded. The capsules must be swallowed whole and must not be chewed or broken.

5.3.1. Treatment Compliance

The study drugs will be dispensed only to eligible subjects and administered under the supervision of study personnel. Treatment compliance will be verified according to the site's standard operating procedures (SOPs).

5.4. Meals

Food intake will be controlled during the confinement period and for all subjects.

Following an overnight fast of at least 10 hours, subjects will receive a standardized high-fat meal 30 minutes before drug administration. The meal will consist of 2 eggs fried in butter, 2 strips of bacon, 2 slices of toast with butter, 4 ounces of hash brown potatoes, and 8 ounces of whole milk. Substitutions in this test meal may be made provided that the meal delivers a similar amount of calories from protein, carbohydrate, and fat and has comparable meal volume and texture. Subjects must eat the total content of this meal in 30 minutes or less. A subject who eats less than 75% of the high-fat meal will be removed from the study. A standardized lunch will be served at least 4 hours after dosing.

5.5. Fluids

Fluid intake other than water will be controlled during the confinement period and for all subjects.

Water will be permitted as needed except from 1 hour predose until 1 hour after dosing.

5.6. Other Protocol Restrictions

Subjects will not engage in strenuous activity at any time during the confinement periods.

6. STUDY PROCEDURES

An overview of the study activities for each participant is detailed in [Table 6-1](#).

Subjects may leave the clinical site 48 hours following drug administration. However, they may be advised to stay at the clinical site for safety reasons, if judged necessary by an Investigator or delegate in charge. Subjects will return to the clinical site for a Follow-Up Visit on Day 7 ± 2.

Unless otherwise stated in the protocol, the SOPs of the study facilities, which are available for all activities relevant to the quality of the study, will be followed during this study. When the nominal time for multiple events occurs simultaneously, the events will be staggered using their acceptable windows (acceptable windows for each assessment are specified in the following sections of this protocol). When timepoints coincide, procedures should be carried out in the following order:

1. Vital signs (prior to nominal time)
2. ECG (prior to nominal time)
3. PK blood sampling (at nominal time)
4. Pupillometry (following nominal time, immediately following PK blood sampling and prior to other PD assessments)
5. Subjective measures (following nominal time, immediately following pupillometry)

Any deviation from protocol procedures should be noted in the source documentation and compiled for reporting in the Clinical Study Report.

Table 6-1. Schedule of Activities

Day	Screening	Treatment Period			Follow-Up Visit	
		-1	1	2	3	7 ± 2 (EOS/ET)
Subject Review						
Informed Consent ^a	X					
Eligibility Criteria Review	X	X	X			
Demographics	X					
Medical History	X	X				
Medication, Recreational Drug, Alcohol, and Nicotine Use History	X	X				
DSM-5 Diagnostic	X					
Safety						
C-SSRS Questionnaire ^b	X	X			X	X
Height, Weight, and BMI ^c	X					X
Blood Pressure, Pulse, Body Temperature, and Respiratory Rate ^d	X	X	X	X	X	X
Continuous SpO ₂ Monitoring ^e			X			
Spot SpO ₂ ^f	X		X			
Physical Examination ^g	X	X			X	X

^a The latest version of the consent form must be signed prior to subject's inclusion (prior to study drug administration).

^b Details presented in Section [6.1.7](#).

^c At the Follow-Up Visit, only weight and BMI will be measured.

^d Timepoints of each parameter (blood pressure, pulse, body temperature, and respiratory rate) are detailed in Section [6.1.4.1](#).

^e Continuous monitoring will be performed up to 1 hour prior to study drug administration and will continue for up to 6 hours following study drug administration, or longer if deemed medically necessary. Additional details are presented in Section [6.1.4.2](#).

^f Timepoints are detailed in Section [6.1.4.2](#) for spot SpO₂.

^g A full physical examination will be performed at Screening and at EOS/ET. A symptom-oriented physical examination will be performed as needed at all other timepoints.

Day	Screening	Treatment Period				Follow-Up Visit
		-1	1	2	3	
General Biochemistry, Hematology, and Urinalysis ^h	X	X			X	X
Lipid Profile ^h	X					X
Serology ^h	X					
12-lead ECG ⁱ	X	X	X	X	X	X
Alcohol and Drugs of Abuse Screen ^h	X	X				
Pregnancy Test ^h	X	X			X	X
FSH ^h	X					
AE Monitoring	X	X	X	X	X	X
Concomitant Medication Recording	X	X	X	X	X	X
Pharmacokinetics						
Blood sampling for PK ^j			X	X	X	
Pharmacodynamics						
Training Session ^k		X				
Pupillometry ^l			X	X		
Subjective Measures ^m			X	X		
Confinement and Study Administration						
Admission		X				
Randomization			X			

^h Details are provided in [APPENDIX 6](#).

ⁱ ECG scheduled timepoints are detailed in Section [6.1.5](#).

^j Blood sampling time points for PK determinations are detailed in Section [6.2](#).

^k Details are presented in Section [6.3](#). Additional training sessions may be conducted as needed.

^l Pupillometry time points for PD evaluations are detailed in Section [6.3.1](#).

^m Type of subjective measures and timepoints are detailed in Section [6.3.2](#).

Day	Screening	Treatment Period			Follow-Up Visit
	-28 to -1	-1	1	2	3
Study Drug Administration			X ⁿ		
Discharge ^o					X

Abbreviations: BMI = body mass index; C-SSRS = Columbia Suicide Severity Rating Scale; DSM-5 = Diagnostic and Statistical Manual of Mental Disorders, 5th Edition; ECG = electrocardiogram; EOS = end of study; ET = early termination; FSH = follicle stimulating hormone; PD = pharmacodynamic; PK = pharmacokinetic; SpO₂ = respiratory rate.

ⁿ Study drug will be administered 30 minutes after the start of a meal as detailed in Section 5.4.

^o Discharge from the clinical site will occur after the 48-hour PK blood sample.

6.1. Safety Assessments

Safety assessments will include AEs monitoring, laboratory tests, vital signs (blood pressure, pulse, respiratory rate, oxygen saturation, and body temperature), ECG assessments, physical examination findings, and C-SSRS. At the discretion of an Investigator, additional safety assessments may be performed as needed to ensure subject safety.

An Investigator or delegate in charge will be present at the clinical site for at least the first 4 hours following drug administration and will remain available at all times throughout the study.

6.1.1. Medical History

The medical history at Screening will include all queries by the medical and clinical staff related to the subject's well-being and history of relevant past medical events/experiences. Medical history will include all demographic data (age, sex, race, body weight, height, and BMI) and baseline characteristics. Alcohol and smoking habits will also be recorded.

6.1.2. Medication, Recreational Drug, Alcohol, and Nicotine Use History

6.1.2.1. Medication Use

Medication history will be collected as scheduled in [Table 6-1](#).

6.1.2.2. Recreational Drug Use

A lifetime history of all recreational drug use will be collected as scheduled in [Table 6-1](#). History, including drug preference (i.e., drug of choice), frequency of use, and date of last use will be collected using reported drug names and drug class (e.g., cannabinoids, depressants, dissociative anesthetics, hallucinogens, opioids, and morphine derivatives, and stimulants).

The DSM-5 modules will be included as a part of the recreational drug use history and used to screen for substance disorder.

6.1.2.3. Alcohol and Nicotine Use

A lifetime history of alcohol and nicotine use will be collected as scheduled in [Table 6-1](#). History, amount, and frequency of use will be collected.

DSM-5 modules will be included as a part of the alcohol use history and used to screen for alcohol disorder.

6.1.3. Physical Examination

A physical examination will be performed by a medically qualified and licensed individual as outlined in [Table 6-1](#).

The full physical examination will include a general review of the following body systems (at minimum): head and neck, cardiovascular, respiratory, gastrointestinal, brief neurological and general appearance, unless a symptom-oriented physical exam is indicated.

6.1.4. Vital Signs

Windows for blood pressure, pulse, body temperature, spot SpO₂, and respiratory rate assessments are presented in [Table 6-2](#). Vital signs will be performed after the subject is in supine position for at least 3 minutes.

Table 6-2. Acceptable Windows for Vital Sign (Blood Pressure, Pulse, Body Temperature, Spot Oxygen Saturation, and Respiratory Rate) Assessments

Elapsed Time	Acceptable Window
Predose	Within 60 minutes prior to study drug administration
> 0 hour and ≤ 24 hours	± 30 minutes
> 24 hours and ≤ 48 hours	± 1 hour

6.1.4.1. Blood Pressure, Pulse, Body Temperature, Respiratory Rate

Blood pressure, pulse, body temperature, and respiratory rate measurements will be measured as outlined in [Table 6-1](#) and are further detailed in [Table 6-3](#).

Table 6-3. Vital Sign (Blood Pressure, Pulse, Body Temperature, and Respiratory Rate) Recording Schedule

Vital Sign Recording - Scheduled Time Points	Detail of Measures
Screening	Blood pressure, pulse rate, body temperature, and respiratory rate
Day -1	Blood pressure, pulse rate, and body temperature
Day 1: predose	Blood pressure, pulse rate, body temperature, respiratory rate
Day 1: 1, 2, 4, and 6 hours postdose	Blood pressure, pulse rate, and respiratory rate
Day 2: 24 hours postdose	Blood pressure and pulse rate
Day 3: 48 hours postdose	Blood pressure and pulse rate
Follow-up visit/End of Study	Blood pressure and pulse rate

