While there are extensive reports in the literature regarding the use of kratom in the US, Malaysia, and Thailand, overall, the available clinical literature is not strong. Most of the published studies on kratom use are not controlled or prospective. There are very few studies directly correlating specific doses of kratom with adverse effects. Rather, there are a large number of case reports available. However, many of the patients described in these cases had a history of chronic kratom use, consumed large amounts of kratom, and/or used multiple substances simultaneously. The case reports cover the years 2010 to 2021. There are a fair number of studies reported in the literature, but they are mostly retrospective analyses of poison center databases, case study series, autopsies, and social media posts, as well as survey (self-reported information) and interview (conducted by trained professional) studies. There are a few small prospective pharmacokinetics studies and in vitro pharmacokinetics studies. The reported studies cover the years 1998-2021.¹

The available literature describing human PK and metabolism studies with kratom are summarized in the Investigator's Brochure of kratom.¹

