1.4. Risk/Benefit Assessment

1.4.1. Known Potential Risks

The true incidence of adverse reactions associated with the use of kratom is difficult to determine, due to the lack of randomized, controlled clinical studies. However, the adverse events (AEs) most commonly reported related to kratom use, in 10% or more of populations identified in published, peer-reviewed articles, are as follows: acute kidney injury, agitation, altered consciousness, anxiety, apathy, appetite loss, blood pressure increase (delayed onset), confusion, constipation, diaphoresis/feeling hot, depression, dizziness, drowsiness/lethargy/fatigue, dyspnea, hallucinations, headaches, heart rate increase (delayed onset), hypotension, hypertension, insomnia, feeling intoxicated, irritability, elevated low-density lipoprotein and high-density lipoprotein, libido/sexual performance decrease, miosis, decreased motivation, mydriasis, nausea, palpitation, physical pain, respiratory failure, stomach ache/abdominal pain, tachycardia, tongue numbness, tremor, weight loss, and vomiting.¹

The doses of kratom administered in this study are not anticipated to induce unmanageable risks to the subjects. The safety monitoring practices employed in this protocol (i.e., AE questioning, clinical laboratory assessments, vital signs [blood pressure, pulse, respiratory rate, oxygen saturation and body temperature], electrocardiogram [ECG], physical examination findings, and Columbia Suicide Severity Rating Scale [C-SSRS]) are appropriate to protect the subjects' safety and should detect treatment--emergent AEs (TEAEs).

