2. STUDY OBJECTIVES AND ENDPOINTS

The objectives and endpoints of the study are presented in [Table 2-1](#).

Table 2-1. Study Objectives and Endpoints

OBJECTIVES	ENDPOINTS
Primary	
To evaluate the safety and tolerability of single ascending oral doses of kratom relative to placebo when administered in healthy nondependent recreational polydrug users with opioid experience.	Safety will be evaluated through the assessment of AEs, laboratory tests, vital signs (blood pressure, pulse, respiratory rate, oxygen saturation, and body temperature), ECGs, physical examination findings, and C-SSRS.
Secondary	
To evaluate the PK of mitragynine, 7-hydroxy-mitragynine, paynantheine, speciogynine, and peciociliatine following single ascending oral doses of kratom in healthy nondependent recreational polydrug users with opioid experience.
 
The PK endpoints of this study are the following PK parameters of mitragynine, 7-hydroxy-mitragynine, paynantheine, speciogynine, and peciociliatine: C_{max}, T_{max}, AUC_{0-T}, and $AUC_{0-\infty}$. Additionally, dose-normalized PK parameters C_{max}/D, AUC_{0-T}/D, and $AUC_{0-\infty}/D$ will be estimated.
 
To evaluate the PD of single ascending oral doses of kratom in healthy nondependent recreational polydrug users with opioid experience.
 
The PD endpoint of this study is the maximum (peak) effect (E_{max}) over 24 hours for Drug Liking (“at this moment”), assessed on a bipolar (0 to 100 points) VAS.
 
Key secondary PD endpoints are:
 
• Overall Drug Liking VAS (E_{max})• Take Drug Again VAS (E_{max})• High VAS (E_{max}) 
Non-key secondary PD endpoints are:
 
• Balance of Effects
○ Drug Liking VAS (minimum effect [E_{min}], time of maximum effect [TE_{max}], time of minimum effect [TE_{min}], and time-averaged area under the effect-time curve [TA_AUE])• Positive Effects
○ Good Effects VAS (E_{max}, TE_{max}, and TA_AUE)○ High VAS (E_{max}, TE_{max}, and TA_AUE)• Negative Effects
○ Bad Effects VAS (E_{max}, TE_{max}, and TA_AUE)• Other Subjective Effects

OBJECTIVES	ENDPOINTS

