6.1.4.2. Continuous and Spot Oxygen Saturation

Continuous and spot SpO₂ monitoring will be performed as outlined in [Table 6-1](#). Spot SpO₂ will be measured using a portable pulse oximeter placed on the subject's fingertip.

SpO₂ will be monitored for alarms set at <90% continuously up to 1 hour prior to study drug administration and will continue for up to 6 hours following study drug administration, or longer if deemed medically necessary. In addition, SpO₂ will be recorded at the timepoints scheduled in [Table 6-4](#).

Table 6-4. Spot Oxygen Saturation Schedule

Spot Oxygen Saturation - Scheduled Time Points
Screening
Day 1: predose and approximately 1, 2, 3, 4, 6, 7, 8, 10, and 12 hours postdose

6.1.5. 12-Lead Electrocardiogram

Twelve-lead ECGs will be performed as outlined in [Table 6-1](#). Electrocardiogram measurements are further detailed in [Table 6-5](#). Subjects will be in supine position for at least 3 minutes prior to ECG measurements.

Table 6-5. Electrocardiogram Recording Schedule

Electrocardiogram Recording - Scheduled Time Points
Screening
Day -1
Day 1: 1 and 4 hours postdose
Day 2: 24 hours postdose
Day 3: 48 hours postdose
Follow-up visit/End of Study

Windows for ECG assessments are presented in [Table 6-6](#).

Table 6-6. Acceptable Windows for Electrocardiogram Assessments

Elapsed Time	Acceptable Window
> 0 hour and \leq 24 hours	\pm 30 minutes
> 24 hours and \leq 48 hours	\pm 1 hour

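### Blood pressure and pulse have no scheduled reading between 6 and 24 hours after dosing, although the protocol lists delayed-onset rises in both and staff already see subjects at 8, 10 and 12 hours

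*Protocol*

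**What the plan says.** Table 6-3 in Protocol section 6.1.4.1 schedules blood pressure and pulse at predose, then "Day 1: 1, 2, 4, and 6 hours postdose", then at 24 and 48 hours and at follow-up. The SAP adds no later reading: its Appendix A points back to the same protocol section for the times. Table 6-5 places postdose ECGs at 1, 4, 24 and 48 hours.

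Section 1.4.1 includes among the commonly reported events "blood pressure increase (delayed onset" and "heart rate increase (delayed onset". Hypertension and tachycardia are separate entries in the same list. No length of delay is given. Section 1.2 says of the evidence base: "There are very few studies directly correlating specific doses of kratom with adverse effects".

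Other assessments run later than 6 hours. Spot oxygen saturation is scheduled at "Day 1: predose and approximately 1, 2, 3, 4, 6, 7, 8, 10, and 12 hours postdose" (Table 6-4). PK samples (Table 6-7), pupillometry (Table 6-9) and the repeated subjective scales (Table 6-11) are each due at 8, 10 and 12 hours. Subjects stay on site until 48 hours (section 3.1).

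On analysis, SAP 5.1 summarises non-AE safety data by dose level and pooled placebo and keeps unscheduled assessments out of the descriptive summaries except for baseline. SAP 10.3 summarises vital signs by treatment and by visit and/or time point, and lists all readings.

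**The concern.** The primary objective is "To evaluate the safety and tolerability of single ascending oral doses of kratom relative to placebo", and vital signs are a named part of that endpoint. The protocol identifies a delayed haemodynamic effect as a risk, then stops measuring blood pressure and pulse at 6 hours until the next morning. It gives no reason for stopping there, while oxygen saturation continues to 12 hours and the PD scales to 24.

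The at-risk case is narrow: a rise that begins after 6 hours, resolves before 24 hours, causes no symptoms and prompts nobody to take a reading. Such a rise would reach neither the AE tables nor the vital-sign tables. If a reading were prompted, it would be listed and the Safety Review Committee could see it. It would still not enter the by-treatment summaries, and readings taken because someone noticed something are not a fair comparison of active with placebo.

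The stakes are descriptive. Escalation need not turn on these tables, because the stopping and MTD rules (sections 3.3 and 4.3.2) count adverse events and serious adverse events. What would be lost is information on late haemodynamic effects in a study meant to inform later kratom research and dose choice.

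**Working it through.** The plan states no figure of its own on this point, so the check compares the schedules and measures the gap.

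**Scheduled times strictly between 6 and 24 h**

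| Assessment | Source | Times |
|---|---|---|
| Blood pressure, pulse | Table 6-3 | none |
| ECG | Table 6-5 | none |
| Spot SpO2 | Table 6-4 | 7, 8, 10, 12 h |
| PK blood sample | Table 6-7 | 8, 10, 12 h |
| Pupillometry | Table 6-9 | 8, 10, 12 h |
| Repeated subjective scales | Table 6-11 | 8, 10, 12 h |

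The saturation readings use a pulse oximeter, but only SpO2 is scheduled to be recorded, not pulse.

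**Gap** (window ±0.5 h, Table 6-2)

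- Now: 24 − 6 = 18 h. Shortest 23.5 − 6.5 = 17 h; longest 24.5 − 5.5 = 19 h. Share of the first day: 18/24 = 75%. Postdose readings to 24 h: 1, 2, 4, 6, 24, so 5.
- With 8, 10 and 12 h added: 24 − 12 = 12 h. Shortest 23.5 − 12.5 = 11 h; longest 24.5 − 11.5 = 13 h. Share: 12/24 = 50%. Postdose readings to 24 h: 8.

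Share of clock time describes coverage. It is not a measure of risk.

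**Illustration of detection.** This is an assumption, not taken from the documents: a rise lasts d hours, lies wholly between 6 and 24 h, and its start s is uniform on [6, 24 − d]. Under the present schedule detection is 0% by construction. With readings at 8, 10 and 12 h it is seen if at least one of those times falls in [s, s + d].

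| d | Starts that are caught | Detection |
|---|---|---|
| 1 h | 7–8, 9–10, 11–12: 3 h of 17 | 3/17 = 17.6% |
| 2 h | 6–12: 6 h of 16 | 6/16 = 37.5% |
| 4 h | 6–12: 6 h of 14 | 6/14 = 42.9% |
| 6 h | 6–12: 6 h of 12 | 6/12 = 50% |

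If each reading time varies uniformly within ±0.5 h, only the 2 h figure moves. The expected length of caught starts falls by 1/8 at the lower edge and by 1/6 at each of two joins: 6 − 1/8 − 2/6 = 5.54, and 5.54/16 = 35%.

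At nominal times, any rise that starts between 6 and 12 h and lasts at least 2 h meets a reading. A rise wholly inside 12–24 h is still missed.

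**Cost.** 40 subjects × 3 times = 120 sets: 30 active × 3 = 90 and 10 placebo × 3 = 30. At the 3-minute supine minimum, 120 × 3 = 360 minutes, or 6 h of subject time over the study. This leaves out the time to measure and record.

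**The case against.** The strongest reply is that everything rests on one undefined phrase. The delayed-onset wording is referenced to the Investigator's Brochure, which may give the delay and may be the basis for the 6-hour cut-off. Section 1.2 adds that many published cases involved chronic use, large amounts or several substances, so the delay may not carry over to one supervised dose. This stands as a limit: the documents do not show onset after 6 hours. They do not exclude it either, and they give no reason for stopping at 6.

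Second, the schedule is not blind to late effects. Readings at 6, 24 and 48 hours catch any rise present then. Subjects are confined and supervised by nurses or paramedics, and extra assessments are allowed (sections 6.1 and 6.1.8). A rise reported as an AE is tabulated by dose and pooled placebo. All of this is right for symptomatic or noticed cases. It does not help with a rise that nobody measures. Section 7.4 fixes health questioning only at the start of a study period and before departure, and on-site presence of the investigator or delegate is guaranteed only for the first 4 hours.

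Third, SAP 5.1 goes on to say that, for repeated or unscheduled assessments, the result nearest dosing enters the summary tables. That makes the rule less clean than its opening sentence. Even so, it does not supply a row for an interval with no scheduled time point.

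Fourth, the detection figures assume the rise lies inside the gap, and uniform onset has no support in the documents. That is fair. They illustrate what three readings would buy and predict nothing about this trial. They also show that half or more of the modelled rises of 6 hours or less would still escape in most cases, with detection reaching only 50% at 6 hours.

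**Conclusion.** The point holds as an inexpensive improvement worth considering, held with medium confidence. It is a matter of fact that blood pressure and pulse have an 18-hour scheduled gap (17 to 19 with windows), that both are listed with delayed-onset rises of unstated delay, and that contacts already exist at 8, 10 and 12 hours. Whether the gap hides anything depends on an onset time the documents do not give. If the rise always appears by 6 hours and persists to a scheduled reading, nothing is lost. If it can start later and resolve before 24 hours without symptoms, the present schedule cannot see it and the placebo comparison has no data for that interval. Neither the stopping rules nor the MTD definition is affected, and the analysis is descriptive with 6 active subjects per dose.

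**What to change.** Add one row to Table 6-3: blood pressure and pulse at 8, 10 and 12 hours postdose. Respiratory rate could be added as a minor extra, since spot SpO2 already gives partial respiratory cover to 12 hours.

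No new contact time or visit is needed. Section 6 already puts vital signs first in its sequence ("When timepoints coincide, procedures should be carried out in the following order"), and the ±30 minute vital-sign window leaves room to finish before the PK draw, which has ±5 minutes at these times. Make explicit in SAP 10.3 that vital signs are summarised at each scheduled time point, because its present and/or wording does not guarantee it. The new readings would then be compared with pooled placebo.

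The burden is three sets per subject. Section 6.1.4 sets the minimum for each: "Vital signs will be performed after the subject is in supine position for at least 3 minutes". The real downside is that the 8, 10 and 12 hour contacts become busier. The change shortens the gap but does not close it, since the protocol schedules no contact between 12 and 24 hours. If the Brochure does give a delay that fits inside 6 hours, a sentence in the protocol saying so would be an acceptable alternative.
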